Date: 02.06.2023

A PILOT STUDY ON THE MICROBIOLOGICAL DIVERSITY IN ORAL LICHEN PLANUS (OLP)

[name], [name], [name], [name], [name]

APPROACH AND METHODS TO BE APPLIED:

Seven individuals who presented to the M.U. Faculty of Dentistry, Department of Oral and Maxillofacial Radiology Clinic and were diagnosed with "OLP" clinically and histopathologically (mucosa with OLP lesions and healthy mucosal tissue from the same patient) will constitute the patient group. Six healthy individuals who agreed to participate in the study and who presented to our clinic due to any complaints and who do not have any autoimmune symptoms will constitute the control group.

Clinical Examination:

1. Systemic and dental histories will be obtained for all patients included in the study.
2. Oral mucosal and dental examinations will be performed for all patients included in the study. The location and type of lichen planus lesions, the type and condition of the dentures (if any), and the type and distribution of dental materials will be assessed and recorded on the "Patient History and Evaluation Form."

Sample Collection

1. Three samples will be collected from patients with OLP: Two from oral lichen planus lesions (OLP) located on the buccal mucosa and one from unaffected oral mucosa (vestibular sulcus or labial commissure) (H-OLP).
2. Two samples will be collected from healthy patients: Two from bilateral healthy buccal mucosa (H).

Participants will be advised to brush their teeth and avoid food intake for at least one hour before sampling.

A 50 mg tissue sample will be collected from the patients using a cytobrush and transferred to 2.0 ml centrifuge tubes. The tubes will be stored at -80°C for DNA extraction.

DNA Isolation

DNA extraction will be performed using the QIAamp DNA Mini Kit (Qiagen) using the QIAcube Lt automated isolation device, according to the manufacturer's protocol. A 50 mg tissue scraping sample will be homogenized in 200 μ L of 0.9% NaCl before adding proteinase K and lysis buffer, following the Purelink protocol. Isolated DNA will be measured at A260 absorbance using a Nanospectrophotometer (QIAxpert). If DNA amounts exceed 30 ng/ μ L, samples will be submitted for microbiota analysis.

Microbiota analysis

Targeted amplification from total genomic DNA will be performed using metabarcoding library construction using specific rDNA primers, equimolar pooling, MiSeq high-throughput sequencing (Illumina, San Diego, CA, USA), and multiplexing of paired-end reads (2 \times 300 bp).

Paired-end sequences will be clustered using the swarm clustering method, with a maximum of 3 allowed differences between amplicons ($d = 3$). All clusters will be filtered for chimeras using VSEARCH. Operational Taxonomic Units (OTUs) with an abundance of less than 0.005% will be discarded because they are more likely to be chimeras from rare clusters. Finally, the affiliation of all bacterial OTUs will be verified using sequences from type material in the EzBioCloud database and the 16S rRNA and ITS databases for BlastN at NCBI. Remaining identified chimeras will be manually filtered, and these improved OTU tables will be used to calculate biostatistics using the PhyloSeq R package v1.28.0 implemented in FROGS. Alpha-diversity metrics (Chao1 and inverse Simpson indices) will be calculated after rarefaction. The abundance-based dissimilarity (beta-diversity) index, the Bray-Curtis index, will also be calculated after rarefaction. Microbiota analysis will be performed as a service outsourced.

ANTICIPATED WORK DURATION: 1 year

Start date: June 15, 2023

Data evaluation period: 9 months

End date: March 15, 2024

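### Autoimmune symptoms are barred in controls only, so the OLP vs H and H-OLP vs H contrasts may be confounded by unscreened autoimmune comorbidity in patients

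*Combined protocol and SAP*

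**What the plan says.** The entry rules stand in adjacent sentences under 'Approach and methods to be applied' in the combined protocol and SAP. Seven people who "were diagnosed with 'OLP' clinically and histopathologically (mucosa with OLP lesions and healthy mucosal tissue from the same patient) will constitute the patient group". No other health condition is set for them. The comparison group is "Six healthy individuals who agreed to participate in the study and who presented to our clinic due to any complaints", with the further condition that they are people "who do not have any autoimmune symptoms will constitute the control group".

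Under 'Clinical Examination', item 1, "Systemic and dental histories will be obtained for all patients included in the study". The plan does not use these histories for patient entry, matching, adjustment or a sensitivity analysis.

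Under 'Sample Collection', each patient gives two samples from buccal lesions (OLP) and "one from unaffected oral mucosa (vestibular sulcus or labial commissure) (H-OLP"). For controls, "Two samples will be collected from healthy patients: Two from bilateral healthy buccal mucosa (H").

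Under 'Microbiota analysis', "Alpha-diversity metrics (Chao1 and inverse Simpson indices) will be calculated after rarefaction", and the Bray-Curtis index is handled the same way. No test between groups is named. The contrasts discussed here are implied by the patient and control groups and by the three sample labels.

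**The concern.** Autoimmune status is the one specific health criterion that the plan names, and it is applied to one group only. If other autoimmune disease, or long-term treatment for it, alters the oral microbiota, then a difference between patients and controls has two possible explanations: OLP itself, or a comorbidity that was screened out of the controls and not out of the patients.

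This matters for both between-person contrasts. OLP vs H is the site-matched one, buccal against buccal. H-OLP vs H is the one that might suggest a mouth-wide change in people with OLP. A systemic condition could act on unaffected mucosa as well as on lesions, so it could produce a difference in either contrast without OLP being the cause.

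**Working it through.** The plan gives no figure on this point to reproduce: no prevalence of comorbidity, no effect size, no SD and no derivation of the group sizes. The check is therefore a comparison of the text, followed by an illustration under stated assumptions.

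**Text, side by side**

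| | Patients | Controls |
|---|---|---|
| Number | 7 | 6 |
| Positive entry condition | OLP, clinical and histopathological | Healthy, attending the same clinic |
| Autoimmune filter | None stated | No autoimmune symptoms |
| Systemic history | Taken, no stated use | Taken, no stated use |

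**Which contrasts are exposed**

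- OLP vs H: between people, same site. Exposed.
- H-OLP vs H: between people, and the sites also differ (vestibular sulcus or labial commissure against buccal mucosa). Exposed, on top of the site difference.
- OLP vs H-OLP: within the same patient, so autoimmune status and systemic treatment are constant. Not exposed, though the sites differ.

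**Weight of one affected patient (from the plan's numbers)**

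- Share of the patient group: 1/7 = 14%.
- Patient samples planned: 7 × (2 + 1) = 21. One patient supplies up to 3 of them. This is a maximum, because under 'DNA Isolation' a sample goes forward only if its DNA exceeds 30 ng/μL.

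**Chance that at least one of 7 patients is affected (prevalence p assumed)**

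Formula: 1 − (1 − p)^7.

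| Assumed p | Chance of at least one |
|---|---|
| 5% | 30% |
| 10% | 52% |
| 20% | 79% |
| 30% | 92% |

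**Shift in an alpha-diversity mean (number affected k and effect D assumed)**

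With one value per person, the patient-group mean moves by (k/7) × D. For D = 1 SD:

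- k = 1: 1/7 = 0.14 SD
- k = 2: 2/7 = 0.29 SD
- k = 3: 3/7 = 0.43 SD

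The standard error of a difference in means between 7 and 6 people, with equal SDs, is √(1/7 + 1/6) = √0.3095 = 0.56 SD. The shift is thus 0.143/0.556 = 0.26 of a standard error for one affected patient and 0.429/0.556 = 0.77 for three. If no patient has another autoimmune condition, k = 0 and the shift is 0.

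**The case against.** The strongest reply is that the plan has its own safeguard and that the likely bias is small. Each patient supplies an unaffected-mucosa sample, so OLP vs H-OLP is free of this problem. How often the comorbidity occurs is unknown, and any count such as 1 to 3 of 7 is an assumption. One affected patient, even with a full 1 SD effect, moves the mean by about a quarter of a standard error. All of this stands.

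It also stands that the control rule concerns symptoms, so controls are free of other autoimmune disease only as far as symptoms reveal it. Controls must in addition be healthy in general, while patients need not be. An autoimmune filter for patients leaves that wider asymmetry in place. H-OLP vs H would still carry its site difference.

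A reader might go further and infer that the groups are made to differ in all other autoimmune disease, or that the study cannot isolate OLP at all. The documents support neither reading. Patients are not selected for other autoimmune disease; they are only not screened for it, so the groups may differ but need not. The second reading also overlooks the within-patient contrast.

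What the reply does not remove is the one-sided rule itself. Both entry rules are given, and nothing later in the plan corrects for the difference. The within-patient contrast is not a full substitute either, because it sets buccal lesions against a different site.

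**Conclusion.** The point holds as a possible confounder of OLP vs H and H-OLP vs H, not as a demonstrated bias and not as a flaw in every contrast. That the filter applies to controls only rests on the text and needs no assumption. The size does rest on assumptions: the number of affected patients and the effect of their condition are not in the documents. At an assumed effect of 1 SD, the shift is 0.14 SD for one patient and 0.43 SD for three, against a standard error of about 0.56 SD. That is modest for one patient unless the condition's effect is large. These figures concern a mean alpha-diversity index and do not carry over directly to Bray-Curtis. The change is worth making because it is cheap and removes a rival explanation, not because the results would otherwise be unusable.

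**What to change.** Apply the filter to both groups, checked from the systemic history already taken:

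- Patients: no autoimmune disease or symptoms other than OLP.
- Controls: no autoimmune disease or symptoms.

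The words 'other than OLP' are needed because the documents do not say whether OLP itself counts as an autoimmune condition, and copying the control rule unchanged might exclude the patients under study.

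If patients with another autoimmune condition are to be kept, or have already been sampled, record the condition and report OLP vs H and H-OLP vs H with and without them. With 7 and 6 people, adjustment in a model is hardly feasible, so restriction or a with-and-without report is the practical choice.

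The entry rule costs one phrase and no new data collection. Its downside is a slightly smaller pool from which to find seven patients, and results limited to OLP without other autoimmune disease. The with-and-without report avoids both costs but leaves fewer patients in the restricted comparison. Under either option, the requirement that only controls be healthy remains for other systemic illness and should be acknowledged when the between-person contrasts are interpreted.

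### Does a 30 ng/µL DNA threshold with no stated rule for failing samples undermine the lesion versus H-OLP comparison?

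*Combined protocol and SAP*

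**What the plan says.** The plan is short, and four of its sections bear on this point.

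- **Approach and Methods.** There are seven OLP patients and six controls. The patient group is described by its paired tissue: "mucosa with OLP lesions and healthy mucosal tissue from the same patient".
- **Sample Collection.** Each OLP patient gives two lesion samples and "one from unaffected oral mucosa (vestibular sulcus or labial commissure) (H-OLP"). Each control gives two samples. On quantity: "A 50 mg tissue sample will be collected from the patients using a cytobrush".
- **DNA Isolation.** The same quantity goes into extraction: "A 50 mg tissue scraping sample will be homogenized in 200" µL of saline. Then "Isolated DNA will be measured at A260 absorbance using a Nanospectrophotometer (QIAxpert"). The gate follows: "If DNA amounts exceed 30 ng"/µL, "samples will be submitted for microbiota analysis". No other branch is given.
- **Microbiota analysis.** The outputs are Chao1, inverse Simpson and Bray-Curtis after rarefaction. No group comparison or test is named. The section ends: "Microbiota analysis will be performed as a service outsourced".

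**The concern.** The threshold sentence covers only samples that pass. Nothing is said about re-extraction, re-sampling or replacement, or about how to analyse a patient who has lost one side of the pair. The amount collected equals the amount homogenised, so no reserve tissue is described. The measure is also coarse: A260 absorbance counts all nucleic acid, the patient's own included, so a sample can pass or fail for reasons unrelated to its bacteria.

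The sampling scheme makes the gap lopsided. A patient can lose one lesion sample and still contribute a lesion versus H-OLP contrast. A patient who loses the H-OLP sample cannot. With only seven patients, each lost pair matters. Without a written rule, someone might also decide the fate of a weak sample case by case, knowing which tissue it came from.

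**Working it through.** The plan states no sample size calculation, power or failure rate, so there is no figure of its own to reproduce.

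**Inputs from the plan.** Seven OLP patients with 2 lesion + 1 H-OLP samples, and six controls with 2 samples: 7×3 + 6×2 = 33 samples.

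**Assumptions.** Each sample fails the threshold independently with probability *q*, the same for every tissue type, and failing samples are not sequenced. The range 5% to 30% for *q* is assumed; nothing in the document supports one value over another.

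**Formulas.** A patient's pair survives if the H-OLP sample passes and at least one lesion sample passes: *p* = (1−*q*)(1−*q*²). Expected intact pairs are 7*p*. The chance that all seven survive is *p*⁷. The share of broken pairs in which the H-OLP sample failed is *q*/(1−*p*). With two H-OLP samples, expected pairs would be 7(1−*q*²)².

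| *q* | *p* | Expected pairs of 7 | All 7 intact | Broken pairs with H-OLP failed | Expected pairs, two H-OLP samples |
|---|---|---|---|---|---|
| 5% | 0.948 | 6.63 | 69% | 95% | 6.97 |
| 10% | 0.891 | 6.24 | 45% | 92% | 6.86 |
| 20% | 0.768 | 5.38 | 16% | 86% | 6.45 |
| 30% | 0.637 | 4.46 | 4% | 83% | 5.80 |

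**Cost in precision.** For a mean within-patient difference with unchanged variance per pair, the standard error relative to seven pairs is √(7/*n*): 1.08 with 6 pairs, 1.18 with 5 and 1.32 with 4.

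**Sensitivity to independence.** Samples from one mouth may share causes of low yield. At the extreme, where all of a patient's samples pass or fail together, expected pairs are 7(1−*q*) = 6.65, 6.30, 5.60 and 4.90, whether one or two H-OLP samples are taken. The H-OLP share in the table, and any gain from a second H-OLP sample, therefore depend on independence and say nothing about what will happen in this study.

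**Reading the threshold sentence.** The table applies only if low-yield samples are not submitted. On that reading the sentence already decides their fate, and little is left to case-by-case choice. If instead such samples might be sequenced or replaced, the losses in the table do not follow. The two worries cannot both apply at full strength.

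**The case for a change.** The strongest case for a change is that reading the sentence as an implicit exclusion produces exactly the pair loss described and still leaves the incomplete patient unaddressed. Same-patient sampling has little purpose other than a within-patient comparison, so it is fair to judge the plan on one. With so few patients the loss could be decisive: the smallest two-sided *p*-value from an exact signed-rank test is 2/2ⁿ, which is 0.016 with seven pairs, 0.031 with six and 0.0625 with five, so after two lost pairs such a test could not reach 0.05. A few sentences in the protocol would cost almost nothing.

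Part of this stands. The plan does not say what happens to an incomplete patient, and counts of failing samples by tissue type would be useful results from a pilot study. But the signed-rank limit belongs to a test the plan does not name, in a study that states no significance level. The missing wording is of the kind that gets filled in one sensible way: a patient without a usable H-OLP sample cannot enter that comparison, remains available for comparisons with controls, and the number of pairs is reported.

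The remedies that would change the data are harder to defend. Sequencing samples at or below the threshold would empty the threshold of effect and, as no negative controls are described, could add contamination noise. A second H-OLP sample means seven more mucosal samples (33 to 40) for a gain, under independence, of 6.97 − 6.63 ≈ 0.3 pairs at 5% failure and 6.86 − 6.24 ≈ 0.6 at 10%. The gain is larger at 20% or 30% (about 1.1 and 1.3 pairs), but nothing suggests failure is that common, and it vanishes if a patient's samples fail together.

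**Conclusion.** No change follows. The omission is real but small: the plan leaves unsaid something that its own sentence implies and that analysts will complete sensibly. Following it as written gives a valid comparison on whichever pairs remain.

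The size is uncertain because the failure rate is unknown. At 5% per sample, fewer than half a pair is expected to be lost; at 30%, about two and a half. These figures rest on independent, equal failure rates, non-submission of failing samples, and a paired mean difference that the plan does not itself specify. Bias would need yield to be related to diversity and failure to differ between tissue types, and the document gives evidence of neither. Adding samples or sequencing those below the threshold would trade a possible modest loss of precision for extra procedures or noisier data, which is a matter of judgement and not a correction.
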